Restorelle Smartmesh (Coloplast®, Minneapolis, MN, USA) is an ultra-light macroporous polypropylene mesh graft intended for pelvic floor reconstruction. Two grafts are currently made for sacrocolposuspension: the restorelle Y mesh and the restorelle flat mesh (L mesh). The Y mesh has two arms which attach to the anterior and posterior vagina and a stem which attaches to the sacral promontory. The flat mesh is a sheet of polypropylene that comes in three sizes (Restorelle M Flat Mesh - 15cm x 10cm, Restorelle L Rectangle Flat Mesh - 24cm x 8cm, Restorelle XL Flat Mesh - 30cm x 30cm) and can be trimmed into two strips that are attached to the anterior and posterior vagina, respectively, and then sutured together to the sacral promontory. Currently, both types of grafts are used to perform sacrocolpopexy.

Cost of health care has become a hot topic in the medical community. One of the focuses of cost containment in medicine has centered around operating room efficiency. Several studies have looked at OR time nonutilization (7) in order to determine the economic value of saving OR time. Surgeons can make significant contributions to these types of savings by reducing equipment needs, facilitating case set-up times, and focusing on intraoperative efficiency. This includes choosing materials that may make certain procedures faster and more efficient. When performing a sacrocolpopexy, surgeons have the option of choosing a mesh graft configured in a Y shape, which requires introduction into the pelvis only once, and suturing of one arm to the sacral promontory; versus a dual flat mesh, which requires introduction into the pelvis twice, as there are two separate pieces to suture to the vagina, and suturing of both pieces of mesh together to the promontory. It is unclear if one version of the restorelle mesh is faster to use than the other, and if this savings in time, translates to cost savings in the operating room. The primary objective of the proposed study is to determine the difference in suturing time when using the restorelle Y mesh versus the restorelle dual flat mesh at the time of laparoscopic and robotic-assisted laparoscopic sacrocolpopexy.

Hypothesis: Suturing time when using the restorelle Y mesh will be faster than when using the restorelle dual flat mesh at the time of laparoscopic and robotic-assisted laparoscopic sacrocolpopexy.

Study Design: Randomized single-blind prospective clinical trial

Primary Outcomes:

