1. Total Suturing time for mesh placement = time from insertion of Y mesh or first flat mesh arm into pelvis to last sacral suture placed
2. Total OR time = operating room time of entry and exit
3. Total Case time = Incision to end of closure

Secondary Outcomes:

1. Intraoperative, peri-operative and post-operative complications
2. Hospital costs (Y mesh v. dual mesh and stratified by RA LSC v. LSC)
3. Post-operative patient outcomes at 6 weeks, 6 months, 12 months and 24 months
 - Pelvic Organ Prolapse Quantification (POPQ) system (standardized quantification of prolapse established by the International Continence Society) – Required at 6 months; Optional but encouraged at 12 and 24 months.
 - Pelvic Floor Dysfunction Inventory (PFDI-20) – Required pre-operatively and at 6 weeks, 6, 12 and 24 months.

Study Population: Study subjects will be recruited from patients that present to the Center of Urogynecology and Pelvic Floor Disorders in the Department of Obstetrics and Gynecology at the Cleveland Clinic main campus, Hillcrest Hospital and Fairview Hospital, and their surgeries will be performed at either one of these sites.

Inclusion Criteria:

- Age \geq 18, who are to undergo laparoscopic or robotic laparoscopic sacrocolpopexy for pelvic organ prolapse
- Other concomitant laparoscopic or prolapse and anti-incontinence procedures (e.g., laparoscopic supracervical hysterectomy, cystocele repair, rectocele repair or mid-urethral sling procedures) will be performed at the primary surgeon's discretion.

Exclusion Criteria:

- Inability to comprehend written and/or spoken English
- Inability to provide informed consent
- Medical illness precluding laparoscopy
- Need for concomitant surgeries not related to pelvic organ prolapse or incontinence
- Sacrocolpoperineopexy

Study Procedures:

Study Identification and Recruitment

Potential subjects will be identified by members of the Center for Urogynecology and Pelvic Reconstructive Surgery at the Cleveland Clinic main campus and Fairview Hospital. Eligible patients that agree to participate will be provided written informed consent administered by the collaborators listed on this IRB at the Cleveland Clinic main campus and Fairview Hospital.

Randomization

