All subjects will be predetermined by their surgeon to undergo either a laparoscopic or robotic assisted laparoscopic sacrocolpopexy depending upon their clinical evaluation. The participants will then be randomized to either Y mesh or dual flat mesh sacrocolpopexy according to a computer-generated randomization schedule with random block sizes with the use of the SAS statistical software package (SAS Institute, Cary, NC). Randomization will be carried out by provider. All patients will be blinded to their assignment.

Office Interventions

In addition to a standardized evaluation including the history and physical examination, patients will be asked to complete the Pelvic Floor Distress Inventory (PFDI-20) questionnaire at the pre-operative visit as well as the 6 week, 6, 12 and 24 month postoperative visit. Completion of these questionnaire is the only additional assessment that is specific to participation in this study and is not usually included as part of the standard care of sacrocolpopexy. It should take no more than 10-15 minutes to complete the questionnaire. The study subjects will not be exposed to any additional risk by participating in this study except for the inconvenience of completing the questionnaire.

Surgical Interventions

Laparoscopic sacrocolpopexy will be performed using four ports: an umbilical port for the laparoscope, two ports (either 5 or 10/12 mm) in the bilateral lower quadrants, and one 5-mm port placed at the level of the umbilicus, lateral to the rectus muscle on either side for retraction. The robotic-assisted hysterectomy will be performed using the da Vinci Surgical System (Intuitive Surgical Inc., Sunnyvale, CA, USA) using five ports: a 12mm umbilical port for the laparoscopic, two 8 mm robotic ports placed 2cm inferior and 9-10cm lateral to the umbilicus bilaterally, an 8mm robotic port placed in the left axillary line at the level of the umbilicus, and a 8mm or 10/12mm accessory port either in the right upper quadrant approximately 3cm distal from the costal margin, or in the right lower quadrant, 2cm above and medial to the anterior superior iliac spine.

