If a supracervical hysterectomy is to be performed, it will be done in a standard fashion. A uterine manipulator will be placed inside of the uterus. The round ligaments will be transected using cautery. The fallopian tubes and ovaries will be left in situ or removed at the time of hysterectomy depending upon the preoperative decision made between the surgeon and patient. The uterine arteries and cardinal ligaments will be cauterized

laparoscopically. The uterus will be amputated at the level of the internal cervical os and the endocervical canal will be cauterized.

The sacrocolpopexy will also be performed and in a standard fashion. An end-to-end anastomosis (EEA) sizer will be placed in the vagina for manipulation of the apex as well as in the rectum for delineation of the rectovaginal septum. First, the presacral dissection will be performed with a longitudinal peritoneal incision over the sacral promontory and there is identification of the anterior longitudinal ligament. Dissection is then done caudally through the peritoneum and subperitoneal fat down to the level of the posterior cul-de-sac. The vagina is elevated cephalad using the EEA sizer and the peritoneum overlying the anterior vaginal apex is incised transversely, and the bladder is dissected off the anterior vagina using sharp dissection, creating a 4 to 5 cm pocket. If this plane is difficult to establish, the bladder will be filled in a retrograde fashion to find the correct dissection plane. Similarly, the peritoneum overlying the posterior vagina is incised, and dissection is then done overlying the vagina and extending into the posterior cul-de-sac, creating a 4 to 5 cm pocket. Once dissection is complete, the mesh graft is prepared. Subjects will have been randomized to either one of two mesh grafts:

1. Restorelle Y mesh

- The mesh is introduced into the pelvis through one of the ports.
- First, either then anterior or the posterior arm is fixed to the anterior or posterior vaginal wall using 5 delayed- absorbable (PDS) No. 2-0 sutures in an interrupted fashion, 1 to 2 cm apart from each other.
- The opposing arm of the graft is then attached to either the anterior or posterior vaginal wall, depending on which arm was placed first, in a similar fashion using 5 delayed- absorbable (PDS) No. 2-0 sutures in an interrupted fashion, 1 to 2 cm apart from each other.

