- The stem portion of the graft is then brought to the sacral promontory and sutured to the anterior longitudinal ligament using 2 permanent (prolene) No. 0 sutures. The excess mesh is then trimmed.

2. Restorelle dual flat mesh: 2 pieces of 15 x 4 cm mesh

- One mesh arm is introduced into the pelvis through one of the ports.
- The arm is fixed to the anterior or posterior vaginal wall using 5 delayed- absorbable (PDS) No. 2-0 sutures in an interrupted fashion, 1 to 2 cm apart from each other.
- The second mesh arm is then introduced into the pelvis through one of the ports.
- The arm is fixed to either the anterior or posterior vaginal wall, depending on where the first arm was placed, using 5 delayed- absorbable (PDS) No. 2-0 sutures in an interrupted fashion, 1 to 2 cm apart from each other.
- The two arms are then brought to the sacral promontory and sutured together to the anterior longitudinal ligament using 2 permanent (prolene) No. 0 sutures. The excess mesh is then trimmed.

The peritoneum is then closed over the exposed graft with absorbable suture.

Routine cystoscopy will also be performed in order to assess for lower urinary tract injury. A vaginal exam is performed, and an anterior and/or posterior colporrhaphy and perineorrhaphy are performed if needed. Anti-incontinence procedures may also be performed if needed.

**In laparoscopic cases, all suturing will be done extracorporeally while intracorporeal knot-tying technique will be performed in robot assisted laparoscopic cases.

Data Collection & Management:

Preoperative data will include the following:

- Patient age, race, vaginal parity, menopausal state, BMI, prior prolapse surgery, preoperative prolapse stage
- PFDI-20
- Labs (Hb/Hct)

Data points recorded during the procedure will include:

- Total OR time = operating room time of entry and exit
- Total Case time = time from incision to closure
- Total Suturing time = time from insertion of Y mesh or first flat mesh arm into pelvis to last sacral suture placed
- Level of surgeon performing suturing: Attending v. Fellow v. Both
- Concomitant procedures
 - Hysterectomy – Supracervical or Total
 - Anterior Colporrhaphy
 - Posterior Colporrhaphy
 - Perineorrhaphy
 - Midurethral Sling
- Estimated blood loss
- Intraoperative complications
 - EBL > 500cc
 - Vascular Injury
 - Cystotomy
 - Ureteral Injury
 - Bowel Injury - small bowel, large bowel, rectal

Postoperative data will include the following:

- Days in the hospital

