We will use descriptive statistics to show our demographic and baseline data: categorical variables will be presented as n/N (%) with 95% confidence intervals and continuous variables will be presented as mean+/-SD [range]. Y mesh and dual mesh will be compared between the two groups (Y mesh LSC + RA LSC v. Dual mesh LSC + RA LSC). With a continuous outcome and two categorical independent factors, a two-way

analysis of variance will be used to evaluate differences between the groups. The results will be presented in a standard ANOVA table, which should be sufficient to determine if differences exist. A linear regression will be done to demonstrate actual changes in surgical time attributed to each variable. We will control for LSC ASC and RA LSC ASC by performing a logistic regression. Cost utility analysis will be used to compare the differential mean operating room costs with incremental cost effectiveness ratios (ICERs) calculated as appropriate.

Summary of tasks for study:

	Preop	O R	6 wk postop	6 mo f/u	12 mo f/u	24 mo f/u
Informed consent	X					
Demographic data	X					
Randomization	X					
PFDI-20	X		X	X	X	X
POP-Q	X			X	X ¹	X ¹
OR data collection sheet		X				
Review of d/c summary, chart, postop Hct, complications (ER visits, etc)			X	X	X	X

1. **POP-Q – Optional but encouraged at 12 and 24 months.**

References:

3. Porges RF & Smilen SW. Long term analysis of the surgical management of pelvic floor support defect. *Am J Obstet Gynecol* 1994;171:1518–1528.
4. Birch C. The use of prosthetics in pelvic reconstructive surgery. *Best Pract Res Clin Obstet Gyn* 2005;19(6):979-991.
5. Chu CC & Welch L. Characterisation of morphological and mechanical properties of surgical mesh fabrics. *J Biomed Res* 1985;19:903–916.
6. Kaupp HA, Matulewicz TJ & Lattimer GL. Graft infection or graft reaction? *Arch Surg* 1979;114:1419-1423.

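### The plan neither says when the unblinded operating team learns the mesh nor fixes beforehand who sutures, so operator choice can follow the allocation and bias the time outcomes

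*Combined protocol and SAP*

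**What the plan says.** **Timing of allocation.** The table headed "Summary of tasks for study" marks randomisation in the pre-operative column, not the OR column. Surgical Interventions confirms that allocation is already made when the graft is prepared: "Subjects will have been randomized to either one of two mesh grafts". Randomization describes the method ("according to a computer-generated randomization schedule with random block sizes") and adds "Randomization will be carried out by provider" without explanation. No passage says when the surgeon or theatre staff are told the result.

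**Blinding.** Study Design labels the trial "Randomized single-blind prospective clinical trial". Randomization states "All patients will be blinded to their assignment". Data Collection & Management also blinds the provider who does the POP-Q examination. Nothing is said about the surgeon, theatre staff or whoever records the times.

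**Who sutures.** The list of data recorded during the procedure includes "Level of surgeon performing suturing: Attending v. Fellow v. Both". No rule assigns the operator or fixes the choice before allocation is known.

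**What else is done.** Inclusion Criteria leaves "Other concomitant laparoscopic or prolapse and anti-incontinence procedures" to the primary surgeon's discretion. Surgical Interventions describes vaginal repairs and anti-incontinence procedures as done where needed, after the mesh is in place.

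**Outcomes and analysis.** All three primary outcomes are durations. The Hypothesis expects Y mesh to be faster. The Analysis Plan has a two-way ANOVA, apparently with mesh and approach as factors, and a linear regression whose variables are not listed.

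**The concern.** Suturing time depends on who holds the needle as well as on the mesh. If the team knows the mesh when it decides whether attending or fellow will suture, that decision can differ between arms. A difference between operators would then be read as a difference between meshes. The shift can go either way, so it can create a difference or hide one.

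Randomisation does not protect against this, because the choice of operator comes after it. Recording the operator's level does not repair it either: the actual level is a post-randomisation variable that the mesh may have influenced, so adjusting for it is not a clean remedy. The point at which a safeguard works is before the reveal.

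**Working it through.** **1. Which route reaches which outcome.** Suturing time runs from insertion of the first mesh piece to the last sacral suture. Case time runs from incision to end of closure, and OR time from room entry to exit, so both contain the suturing window.

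- *Choice of operator* acts inside the suturing window (5 + 5 + 2 = 12 sutures in either arm) and so reaches all three outcomes.
- *Concomitant procedures* lie outside it. Hysterectomy is described before the mesh is introduced; vaginal repairs and anti-incontinence procedures come after the last sacral suture. They can move case and OR time only.

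**2. The plan's own figure.** The Analysis Plan gives 9 per arm for a 30-minute difference, 80% power and a significance level of .05, but no SD, so the figure cannot be reproduced forwards. Solved backwards with a two-sided two-sample t-test:

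- Reading 9 as 9 v 9: SD 21.3 gives a noncentrality of 30 / (21.3 × √(2/9)) = 2.99 and power 80%.
- Reading 9 as each of four arms, hence 18 v 18 by mesh: SD 31.2 gives 30 / (31.2 × √(2/18)) = 2.88 and power 80%. At 9 v 9 the same SD would give only 48%.

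Both SDs are carried forward as a range.

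**3. Size of the shift.** Shift = operator gap × difference between meshes in the proportion of cases sutured by the slower operator. Neither quantity is in the documents; both are assumed.

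- 10 min × 0.20 = 2 min
- 10 min × 0.40 = 4 min, and 20 min × 0.20 = 4 min
- 20 min × 0.40 = 8 min

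**4. Effect on the error rate.** The target is 15 × 4 = 60 patients, so 30 per mesh. With no true mesh effect, the rejection rate is that of a two-sided t-test on 58 degrees of freedom with noncentrality shift / SE, where SE = SD × √(2/30). This is 5.50 min at SD 21.3 and 8.06 min at SD 31.2.

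| Shift | SD 21.3 | SD 31.2 |
|---|---|---|
| 0 min | 5% | 5% |
| 2 min | 6.5% | 5.7% |
| 4 min | 11.0% | 7.8% |
| 8 min | 29.9% | 16.4% |

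**5. Concomitant procedures, case and OR time only.** Assume a procedure adding 30-60 minutes, an SD of 45-60 minutes and a 20-point imbalance. The shift is 30 × 0.20 = 6 to 60 × 0.20 = 12 minutes, and the error rate about 7-17%. This treats the whole imbalance as bias, which need not be so.

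**The case against.** **Surgeons cannot be blinded to the device they are suturing.** True, and any effect of knowing the mesh while suturing will remain. What can be avoided is that the operator is chosen with that knowledge.

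**Randomisation by provider already deals with the operator.** The sentence is unexplained. If it means stratification, attendings may be balanced between meshes and part of the route is closed. It still does not fix the attending/fellow split within one provider's cases.

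**The regression can adjust.** Its variables are not listed, and the actual operator level is a post-randomisation variable. This defence does not settle the matter.

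**Three stronger readings are tempting, and the documents do not support them.**

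- A reader might infer that the team knows the mesh early. The task table shows when randomisation happens, not when its result is disclosed; disclosure is unspecified.
- A reader might infer that concomitant procedures bias all three outcomes. They fall outside the suturing window. Moreover, repairs decided after mesh placement may partly be a genuine consequence of the mesh, and those minutes would belong to its effect on case and OR time.
- A reader might infer that only patients are blinded. The POP-Q examiner is too, though this protects none of the time outcomes.

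**The magnitude is hypothetical.** This stands. The 30% figure needs the upper limits of both assumptions together with the smaller SD, and the documents give no reason to expect an imbalance that large.

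**Conclusion.** The concern holds for choice of operator. Allocation precedes surgery, the operating team is not blinded, disclosure is not timed, and no rule fixes who sutures before the mesh is known. The exposed outcome is suturing time, which is the primary objective and the basis of the sample size; case and OR time are exposed through it. For concomitant procedures the concern is confined to case and OR time, and is weaker there.

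The calculated range, a 2-8 minute shift and an error rate of 6.5-30% (SD 21.3) or 5.7-16% (SD 31.2) in place of 5%, rests on an assumed operator gap, an assumed imbalance and back-solved SDs. Its low end is negligible and its high end is not. The documents show an open route without a safeguard; they do not show that the team will use it. It is worth closing because closing it costs little.

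**What to change.** 1. Keep the allocation concealed from the operating team until dissection is complete, the point at which Surgical Interventions has the graft prepared. REDCap, already in use for the study data, is one possible means.
2. Before the reveal, record on the OR data sheet the planned suturing operator (attending, fellow or both) and the planned concomitant procedures. Later departures then become visible.
3. Analyse as randomised. If operator is adjusted for, use the pre-reveal plan and not the actual level, and say so in the Analysis Plan.
4. State what randomisation by provider means.

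**Cost.** Two lines on an existing form, a reveal step in theatre, and both grafts available unopened in the room.

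**Limits.** The reveal does not protect repairs decided after it, a written plan does not prevent a change of operator, and surgeons remain unblinded while suturing.

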- 6-week postoperative visit: PFDI-20
- 6-month postoperative visit (Required): POP-Q exam (performed by a provider blinded to the mesh used at the time of the procedure)
- 12 month, 24 month postoperative visit (Optional): POP-Q exam (performed by a provider blinded to the mesh used at the time of the procedure)
- 6-month, 12-month, 24-month postoperative visit: PFDI-20

- At 6, 12 and 24-months: Review of electronic medical record (inpatient notes, d/c summary, ER visits), assessing for postoperative complications
 - Reoperation for immediate complications = reoperation within 30 days of surgery
 - Abdominal Wound infection = fascial, subcutaneous, cutaneous infection requiring antibiotic treatment
 - Hematoma = intrapelvic/abdominal
 - Vaginal cuff cellulitis/Pelvic Abscess = requiring IV/PO antibiotic therapy and/or transvaginal, transgluteal or percutaneous drainage
 - DVT/PE = diagnosed with Doppler US or CT scan
 - Reoperation for SUI with pubovaginal sling (synthetic or fascial), colposuspension, injection with periurethral bulking agents
 - Reoperation for mesh exposure
 - Reoperation for recurrent POP
 - Bowel Injury/Bowel Obstruction = enterotomy, perforation, ileus, partial/complete obstruction
 - Port site or incisional hernia
 - Need for any radiologic imaging
 - Lower urinary tract injury = bladder, ureteral
 - Neurologic Injury = brachial plexus, abdominal wall (ilioinguinal, iliohypogastric), lower extremity (femoral, sciatic, common peroneal)
 - Pulmonary complications = pneumonia, pulmonary hypertension, pulmonary edema within 14 days of surgery
 - Cardiac = ACS, MI, HF within 14 days of surgery
 - Postoperative ICU admission

[figure not shown]
Protection of each subject's personal health information will be a priority in this study. One master excel file containing subject personal information including name and medical record number will be kept in a password-protected file, on a designated protected research drive on a password-protected computer in a locked office at the Cleveland Clinic. In that file, each subject will be assigned a subject identification number that will be used for the purposes of data collection in order to de-identify subjects.

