All paper forms used for data collection will be kept in a research cabinet dedicated to this project which will be locked at all times, in a locked office at the Cleveland Clinic. All forms will contain de-identified information – identification numbers will correspond to the subjects listed in the master excel file.

All study data will be transferred and managed electronically using REDCap (Research Electronic Data Capture). Each subject will be entered into REDCap using the assigned identification number from the master excel file. REDCap is a secure, web-based application designed to support data capture for research studies, providing user-friendly web-based case report forms, real-time data entry validation, audit trails, and a de-identified data export mechanism to common statistical packages. The system was developed by a multi-institutional consortium which was initiated at Vanderbilt University and includes the Cleveland Clinic. The database is hosted at the Cleveland Clinic Research Datacenter in the JJN basement and is managed by the Quantitative Health Sciences Department. The system is protected by a login and Secure Sockets Layers (SSL) encryption. Data collection is customized for each study as based on a study-specific data dictionary defined by the research team with guidance from the REDCap administrator in Quantitative Health Sciences at the Cleveland Clinic.

Analysis Plan:

There will be 4 arms to this study: laparoscopic (robotic-assisted and conventional) sacrocolpopexy with Y mesh and laparoscopic (robotic-assisted and conventional) sacrocolpopexy with dual flat mesh. Subjects will be chosen based on surgeon preference to either undergo RA LSC ASC or conventional LSC ASC. They will then be randomized to either a Y mesh arm or a Dual Mesh arm. We determined that 9 subjects in each arm were needed to detect a difference of 30 minutes or more in suturing time between the two groups with 80% power and a significance level of .05. We will account for potential subject drop out and loss to follow-up as well as unforeseen factors in recruiting and will plan to recruit 15 subjects to each arm, for a total of 60 subjects.

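### Postoperative complications to 24 months are collected by record review alone, with unclear scope and no question about care elsewhere, so late rates are likely to be understated

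*Combined protocol and SAP*

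**What the plan says.** The Secondary Outcomes list opens with "Intraoperative, peri-operative and post-operative complications". Intraoperative events are recorded during the procedure. For postoperative events, Data Collection & Management specifies "At 6, 12 and 24-months: Review of electronic medical record (inpatient notes, d/c summary, ER visits), assessing for postoperative complications" and then lists the events to look for. One is abdominal wound infection, defined as "fascial, subcutaneous, cutaneous infection requiring antibiotic treatment". Others are vaginal cuff cellulitis (oral antibiotics suffice), stress-incontinence reoperation (which includes periurethral bulking injection), mesh-exposure and recurrent-prolapse reoperation, port-site or incisional hernia, and any radiologic imaging.

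The Summary of tasks describes the review differently: "Review of d/c summary, chart, postop Hct, complications (ER visits, etc", scheduled at 6 weeks as well as at 6, 12 and 24 months.

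On patient contact, Secondary Outcomes says the PFDI-20 is "Required pre-operatively and at 6 weeks, 6, 12 and 24 months". Office Interventions says of it: "Completion of these questionnaire is the only additional assessment that is specific to participation in this study". Data Collection & Management has a "6-month postoperative visit (Required): POP-Q exam" and makes the 12- and 24-month POP-Q examinations optional.

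The Analysis Plan expects losses: "We will account for potential subject drop out and loss to follow-up as well as unforeseen factors in recruiting". It gives no loss rate, and no denominator or missing-data rule for complications. Its n/N convention is stated for demographic and baseline data only.

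**The concern.** The event definitions reach further than the sources named for finding them. A superficial infection treated with tablets, an office bulking injection, an outpatient scan or a hernia seen by another surgeon need not produce an inpatient note, a discharge summary or an emergency visit at the study hospitals. A reoperation at another hospital need not appear in their record at all. Nothing specific to the study asks the woman about such care.

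A record review can be completed for every woman, whether or not she still attends. The record of a woman treated elsewhere can look the same as that of a woman who had no problem. Without a rule separating no event from not observed, the reported rate may mix the two.

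At stake are the absolute complication rates, above all those for late reoperation, hernia and mesh exposure. Events confined to the hospital stay or the first weeks (ICU admission, the 14-day cardiac and pulmonary events, reoperation within 30 days) are less exposed, because the operating hospital is more likely to see them.

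**Working it through.** **The plan's own figure.** There is none to reproduce: the documents give no expected complication rate, no 24-month loss rate and no statement of whether the record shows outside care. The check is therefore a comparison of the sections, followed by an illustration with assumed inputs.

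**Step 1: the two descriptions of the source.**

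| | Data Collection & Management | Summary of tasks |
|---|---|---|
| Timing | 6, 12, 24 months | 6 weeks, 6, 12, 24 months |
| Sources named | inpatient notes, discharge summary, ER visits | discharge summary, chart, postoperative Hct, ER visits, open-ended etc |
| Outpatient or telephone notes | not named | not named; chart could include them |
| Care at other hospitals | not mentioned | not mentioned |

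The two differ in timing and scope. Even on the wider reading, neither provides for care outside the system.

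**Step 2: listed events against those sources.** Skin infection on antibiotics, cellulitis on oral antibiotics, bulking injection, port-site hernia and imaging can be handled wholly in outpatient care. Reoperation for incontinence, mesh exposure or recurrent prolapse carries no time limit in the list and can take place elsewhere.

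**Step 3: size of the understatement.** Let p be the true risk and m the share of women whose events the record cannot show. If they stay in the denominator:

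observed risk = [N(1 − m) × p + N × m × 0] / N = p(1 − m).

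With assumed p = 10%:

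- m = 10%: 0.10 × 0.90 = 9%
- m = 20%: 0.10 × 0.80 = 8%

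The relative understatement equals m. This treats unobservability as unrelated to having an event. If women with problems tend to go elsewhere, the shortfall is larger.

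**Step 4: the comparison between meshes.** With the same m in both groups, the risk ratio does not change: an assumed 15% v 5% at m = 20% becomes 12% v 4%, a ratio of 3 both times, while the difference falls from 10 to 8 points. Unequal m can create a difference: with an assumed true 20% in both groups, m = 10% v 30% gives 18% v 14%. With 60/2 = 30 women per mesh, that is 5.4 v 4.2 expected events, and a single event moves a rate by 1/30 = 3.3 points. Comparative conclusions on complications would be weak in any case, so the argument rests on absolute rates.

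**The case against.** The strongest reply is that the gap is narrower than it looks. The task table's chart review can include outpatient notes, and an event list that contains oral-antibiotic cellulitis suggests that the narrower list of sources is only illustrative. Office Interventions mentions a standardized history and examination alongside the questionnaire visits, so complications may be raised and charted as part of usual care. This is a secondary outcome, and the primary times are complete when the woman leaves the operating room.

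Most of this stands, and it rules out several stronger readings:

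- **Women treated elsewhere or lost to the clinic are counted as complication-free.** A reader might infer this, but no section sets such a rule. What can be said is that classification is unstated.
- **Women are never asked about complications.** The history and examination may apply to the follow-up visits, although the sentence can also be read as the pre-operative visit only. The documents show only that no study-specific question is planned.
- **Outpatient events are excluded from review.** The task table does not support this; the scope is unclear.
- **Loss of 40% is planned for.** The increase from 9 to 15 per arm equals 1 − 9/15 = 40%, but it inflates a sample size for suturing time and also allows for recruitment problems. It is not a forecast of 24-month loss.
- **The mesh comparison is biased.** Nothing in the documents points to different losses by mesh; patients are blinded and the schedule is the same for both.

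What the reply does not remove is care outside the system. Even a full chart review misses it unless the record covers it or the woman happens to mention it, and the plan arranges for neither.

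**Conclusion.** The point holds in a limited form. Record review is the only stated source for postoperative complications, its scope and timing are described inconsistently, and nothing specific to the study captures events managed in outpatient care or at another hospital. With optional examinations at 12 and 24 months, absolute late complication rates are likely to be understated with both meshes.

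The size cannot be derived from the documents. The drop from 10% to 9% or 8% rests on an assumed true risk, an assumed unobservable share of 10% or 20%, keeping those women in the denominator, and unobservability unrelated to events. The direction needs only that some outside events go unrecorded. The point does not touch the three primary time outcomes and does not show bias between the meshes. It is an inexpensive improvement that should be made; it does not threaten the trial's main conclusion.

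**What to change.** 1. Reconcile Data Collection & Management with the Summary of tasks: one list of review times and one list of sources that explicitly includes outpatient and telephone notes.
2. At each required PFDI-20 contact (6 weeks, 6, 12 and 24 months), ask one or two questions about any treatment, imaging, ER visit or reoperation related to the surgery, at any hospital, since the last contact.
3. Report complications with the number of women actually observed, by mesh and time point, and state how women with no later record are handled.

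The cost is a slightly longer form, a few lines of protocol text and smaller late denominators. No extra visit, procedure or recruitment is needed.

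Two limits remain. Women who miss the contacts are still not reached by the questions. Rates among observed women may also run high if those with problems return more often. For example, if all women with an event but only 80% of those without one are observed, an assumed true 10% appears as 0.10 / (0.10 + 0.90 × 0.80) = 0.10 / 0.82 = 12.2%. Showing the number observed beside the number randomized lets the reader judge both directions. The questions must be in place before the contacts take place, because missed information is hard to recover later.
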